Appendix 8: Total Nasal Symptom Score Sheet (Example)

TOTAL NASAL SYMPTOM SCORE

PLEASE ANSWER ALL QUESTIONS TO THE BEST OF YOUR ABILITY. This information will assist us in understanding and treating your symptoms.

1. Please rate how your **nasal congestion** has been over the past: 12 hours Last 2 weeks

None	0 	0 
Mild (symptom clearly present but easily tolerated)	1 	1 
Moderate (symptom bothersome but tolerable)	2 	2 
Severe (symptom difficult to tolerate – interferes with activities)	3 	3 

2. Please rate how your **runny nose** has been over the past: 12 hours Last 2 weeks

None	0 	0 
Mild (symptom clearly present but easily tolerated)	1 	1 
Moderate (symptom bothersome but tolerable)	2 	2 
Severe (symptom difficult to tolerate – interferes with activities)	3 	3 

3. Please rate how your **nasal itching** has been over the past: 12 hours Last 2 weeks

None	0 	0 
Mild (symptom clearly present but easily tolerated)	1 	1 
Moderate (symptom bothersome but tolerable)	2 	2 
Severe (symptom difficult to tolerate – interferes with activities)	3 	3 

4. Please rate how your **sneezing** has been over the past: 12 hours Last 2 weeks

None	0 	0 
Mild (symptom clearly present but easily tolerated)	1 	1 
Moderate (symptom bothersome but tolerable)	2 	2 
Severe (symptom difficult to tolerate – interferes with activities)	3 	3 

5. Please rate how **difficult sleep** has been with nasal symptoms: Last night Last 2 weeks

None	0 	0 
Mild (symptom clearly present but easily tolerated)	1 	1 
Moderate (symptom bothersome but tolerable)	2 	2 
Severe (symptom difficult to tolerate – interferes with activities)	3 	3 

TOTAL SCORE: 0 / 0

## LIST OF ABBREVIATIONS AND TERMS

Abbreviation	Description
ACT	Asthma Control Test
ATC	Anatomical therapeutic chemical
CODIT	Characterized oral desensitization immunotherapy
CoFAR	Consortium of Food Allergy Research
CRF	Case report form
CTCAE	Common Terminology Criteria for Adverse Events
DSMC	Data safety monitoring committee
FAIM	Food allergy independent measure
FAQLQ	Food allergy-related quality of life questionnaire
GI	Gastrointestinal
IgE	Immunoglobulin E
IgG4	Immunoglobulin G subclass 4
MedDRA	Medical Dictionary for Regulatory Activities
OIT	Oral immunotherapy
PERF	Peak expiratory flow rate
PRN	Pro re nata (as needed)
PS	Peanut-specific
QD	Once a day
SAP	Statistical analysis plan
SOC	System organ class
SPT	Skin prick test
SI	Subject identification
TEAE	Treatment-emergent adverse event
TNSS	Total Nasal Symptom Score
WHO-DDE	World Health Organization Drug Dictionary Enhanced

## 1 INTRODUCTION

The purpose of this statistical analysis plan (SAP) is to ensure that the statistical methodologies employed and the final analysis summary tables, figures, and data listings produced will be complete and appropriate to allow valid conclusions regarding the study objectives.

Aimmune Therapeutics, Inc. prepared the SAP, and Precision for Medicine, Oncology and Rare Disease (“Precision”) will perform the analyses and be responsible for the production and quality control of the analysis summary tables, figures, and listings.

This SAP describes the analysis of data collected from ARC007 only. Subjects who received AR101 in study ARC007 and completed the study will have the option to continue treatment with AR101 300 mg once daily (QD) for the duration of the 6-month maintenance period in study ARC011; therefore, a separate SAP or addendum to this SAP will be written to provide a complete safety profile for subjects from initial escalation to the end of the maintenance period for those subjects.

## 2 STUDY OVERVIEW

ARC007 is a multicenter, randomized, double-blind, placebo-controlled safety study of AR101 using the characterized oral desensitization immunotherapy (CODIT™) regimen in peanut-allergic children aged 4 to 17 years, inclusive. The study consists of screening and a double-blind treatment period that includes an initial 2-day escalation and up-dosing (approximately 20-40 weeks). After completion of up-dosing, all study exit procedures, and treatment unblinding, subjects who received AR101 may participate in study ARC011 to receive open-label maintenance treatment with AR101. Subjects who received placebo will be offered up-dosing and maintenance treatment with AR101 in study ARC008.

For additional details on study design and procedures, refer to protocol Section 3 and Section 6.

## 3 STUDY OBJECTIVES

### 3.1 Primary Objective

- The primary objective is to assess the safety and tolerability of AR101 in a CODIT regimen for approximately 6 months of double-blind treatment in peanut-allergic children aged 4 to 17 years, inclusive.

### 3.2 Secondary Objectives

- To characterize the frequency of all treatment-related adverse events by study period
- To assess the effect of AR101 on asthma control and immune parameters

## 4 STUDY ENDPOINTS

Study ARC007 is a safety study; there are no efficacy analyses, and all study endpoints are considered safety endpoints.

### 4.1 Primary Endpoint

The primary endpoint is the frequency of treatment-emergent adverse events, including serious adverse events, during the overall study period.

### 4.2 Secondary Endpoints

Secondary endpoints are as follows:

- Frequency of premature discontinuation of dosing due to adverse events
- Frequency of premature discontinuation of dosing due to chronic/recurrent gastrointestinal (GI) adverse events
- In subjects who discontinue study early due to chronic/recurrent GI AEs, proportion whose ongoing GI adverse events resolved prior to 2, between 2 and 4, between 4 and 12, and  $\geq$  12 weeks following cessation of dosing
- Frequency of allergic reaction (hypersensitivity) adverse events occurring during up-dosing, normalized for duration of treatment
- Frequency of anaphylaxis as defined in the protocol
- Frequency of use of epinephrine as a rescue medication
- Frequency of ingestion of peanut (not study product) and other allergenic foods and severity of any resultant reactions
- Assessment of asthma control using the Asthma Control Test (ACT) questionnaire and frequency of use of asthma rescue medication (short acting beta-agonists) in subjects with asthma
- Frequency of adverse events that lead to early withdrawal

### 4.3 Exploratory Endpoints

The exploratory endpoints are as follows:

- Change in peanut-specific and peanut component-specific serum immunoglobulin (Ig) E and IgG4 levels
- Changes in peanut skin prick test (SPT) mean wheal diameter
- Changes in Total Nasal Symptom Score (TNSS) in subjects with allergic rhinitis

- Changes in scores of the Food Allergy Quality of Life Questionnaire (FAQLQ) and Food Allergy Independent Measure (FAIM)

## 5 SAMPLE SIZE CONSIDERATIONS

ARC007 is a safety study designed to add critical placebo-controlled data to the ongoing safety database of AR101. As such, there are no efficacy endpoints in the study, no specific efficacy-related hypotheses to be tested, and no prospective sample size calculations performed related to the power to detect a prespecified treatment effect size. A sample size of up to 500 subjects randomized in a 2:1 ratio to AR101 or placebo, along with subjects enrolled in other studies in the clinical program was to provide a sufficient number of subjects to fulfill the regulatory requirement for data on at least 600 subjects treated with AR101 at 300 mg/day for 6 months. Randomization was stratified by age group (4-11 years and 12-17 years).

## 6 ANALYSIS POPULATION

### 6.1 Safety Population

The safety population is defined as all subjects who received at least 1 dose of randomized study treatment in ARC007. Subjects will be analyzed according to treatment received.

The safety population of pediatric subjects aged 4 to 17 years will be the population for all analyses unless otherwise specified.

## 7 DEFINITIONS, DERIVATIONS, AND CONVENTIONS

### 7.1 Definitions and Derivations

- Study day is calculated as (assessment date – first dose date + 1) for assessments and visits performed on or after the first dose date, and (assessment date – first dose date) for assessments and visits prior to the first dose date.
- Baseline is defined as the last nonmissing value prior to the first dose of randomized study treatment in ARC007.
- Change from baseline is calculated as the observed value after the first dose – baseline value.
- The screening period is defined as the time beginning with the date and time of informed consent through the day prior to randomization.
- Initial escalation is defined as the time beginning with the date and time of the first dose of randomized study product at the study site and ending with the date of the last dose of randomized study product taken prior to up-dosing.
- Up-dosing is defined as the time beginning with the date and time of the first dose of study product at 3 mg at home, and ending with the date and time of first dose at

300 mg at the study site. Up-dosing will be approximately 20 weeks in duration, but may be extended to a maximum of 40 weeks to accommodate dose reductions and re-escalations, if necessary.

- A 300 mg QD period will be defined as the time beginning with the date and time of the first dose of study product at 300 mg at home and ending with the date of the last dose of study product. This period will be ideally approximately 2 weeks in duration at the end of ARC007, but dosing may continue up to a maximum of 48 weeks after day 1 to ensure tolerability of 300 mg prior to exiting ARC007. Some subjects continued to receive 300 mg doses in ARC007 after the expected rollover date while waiting for activation of ARC008 or ARC011 at the study site. The 300 mg doses as a result of the rollover delay will be included in the 300 mg QD period.

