3.3 Up-Dosing

Subjects will receive IP starting at a dose of 3 mg once daily and will gradually escalate every 2 weeks to a maximum of 300 mg once daily, according to the Up-Dosing Schedule ([Table 2](#)). All first escalation doses will be administered under direct observation in the clinical research center (CRC) or other monitored setting (unless required by a specific institution, no distinction will be drawn between an investigational site, study center office, clinic, or CRC, provided the requirements for monitoring and emergency intervention are met by the facility). Subsequent doses will be dispensed to the parent/guardian and administered at home. Doses may be adjusted for tolerability or inter-current illness by the Investigator, except no down-dosing below 3 mg/day is allowed. The allowed dose levels are shown in [Table 2](#). Up-dosing may thereby be extended to a maximum of 40 weeks in order to reach 300 mg and should not exceed this period.

Subjects unable to escalate to 300 mg within 40 weeks will be considered escalation failures. Subjects able to escalate to 300 mg will continue taking the 300 mg dose for an additional 2 weeks to ensure tolerability prior to exiting ARC007. If the subject is unable to tolerate the 300 mg dose for the 2-week period, dosing may continue up to a maximum of 48 weeks after Day 1 to ensure tolerability prior to exiting the study.

Table 2: Up-Dosing Schedule

Up-Dosing Schedule			
Dose Number	Investigational Product Dose, mg	Interval (weeks)	Percent Increase from Previous Dose
1	3	2 ^a	n/a
2	6	2	100
3	12	2	100
4	20	2	67
5	40	2	100
6	80	2	100
7	120	2	50
8	160	2	33
9	200	2	25
10	240	2	20
11	300	2 ^b	25

^a Interval includes Day 2 of Initial Escalation.

^b If the subject is unable to tolerate the 300 mg dose for the 2-week period, dosing may continue up to a maximum of 48 weeks after Day 1 to ensure tolerability prior to exiting the study.

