6.5.5 Treatment for Reactions During the Up-dosing Period: Dose Adjustment

If a dose or dose level is assessed *as not tolerated*, the action taken will depend on the type and severity of the dose-related reaction and the Investigator's clinical judgment. Dosing must be at a dose level listed in [Table 2](#); dosing below 3 mg/day is not allowed. The following possible actions are at the Investigator's disposal and are considered in greater detail in subsequent sections (Section 6.5.5.1, Section 6.5.5.2, and [Figure 2](#)):

- Dosing the subject under medical supervision in the CRC – this is encouraged whenever there is question as to the tolerability of a dose level. It may be performed at the current dose level or at a reduced dose level, if there is already a high index of suspicion that the current dose level has not been tolerated.
- Holding dose level at current level for an additional 1 to 2 weeks before attempting dose escalation – this may be done at the discretion of the Investigator if there is concern that the current dose level has not been sufficiently well tolerated to attempt up-doing to the next dose level.
- Reducing dose by 1 or 2 dose levels and maintaining the reduced dose level for ≥ 2 - to 4-week period before attempting dose re-escalation – Generally, this should be the

action taken when a dose that has been observed in the CRC is assessed as not tolerated, if a dose elicits moderate or severe reactions that require no more than a single dose of epinephrine for treatment, or if the Investigator is convinced of the intolerability of the current dose level. In short, it should be considered the default action whenever a dose or dose level is assessed *as not tolerated*.

- Reducing dose level for less than the usual 2-week period – this may be instituted as treatment for an inter-current AE, to aid the Investigator in determining if a dose level is or is not tolerated, or if a pattern of decreased IP tolerability during menses is discerned. The level of the reduction in dose, ranging from a 1-step reduction to a 50% reduction will be at the Investigator's discretion, based on clinical judgment. The manner in which dose escalation may resume will depend on the level and the duration of the dose reduction.

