### 9.5 Extent of Exposure and Compliance

Study treatment exposure will be summarized for the safety population by age group (4-11 years, 12-17 years, 4-17 years), treatment group (AR101, placebo) and study period (initial escalation, up-dosing, 300 mg QD, and overall).

First and last dose dates for each study period will be identified as follows:

Study Period	First Dose Date	Last Dose Date
Initial escalation	Date of first dose at the study site on initial escalation day 1	Date of last dose at initial escalation day 1 or day 2 at the study site
Up-dosing	The day following the date study product was dispensed at initial escalation day 2	Date of first dose of 300 mg at the end of the up-dosing 300 mg visit if dose is tolerated and subject continues to at-home 300 mg QD dosing. If first in-clinic 300 mg dose is not tolerated and dose is immediately reduced, the last dose date of up-dosing will be when the first in-clinic 300 mg dose is tolerated and subject continues to at-home 300 mg QD dosing. For subjects who do not reach the 300 mg dose, the latest of the last dose during up-dosing at the study site and the last dose at home
300 mg QD	Date of first dose of study product of 300 mg at home. This is defined as the day following the first in-clinic visit where the 300 mg dose was tolerated and 300 mg study product was first dispensed.	Date of last dose of study product for subjects who enter 300 mg QD study period
Overall	Date of first dose at the study site on initial escalation day 1	Last dose of study product prior to exit visit in ARC007

The total amount of study product consumed will be calculated as the sum of doses at the study site plus the sum of doses taken at home as recorded in the dosing diary.

The following calculations of study product exposure will be made and summarized:

- Duration of exposure (in days and in months): calculated as the date of the last dose of study product minus the date of the first dose of study product plus 1 during the study period, except for initial escalation, the duration of exposure will only be 1 or 2 days depending on whether study product was taken on initial escalation day 1 and initial escalation day 2. Duration of exposure will be summarized using descriptive statistics for continuous endpoints and categorically by 28-day increments for the overall treatment period:  $\leq 28$  days, 29–56 days, ... 337–364 days, and  $> 364$  days.

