### **9.8.1 Adverse Events**

All adverse events recorded on the adverse event case report form, symptoms recorded on the allergic adverse events case report form, and symptoms recorded on the in-clinic dosing case report will be summarized together.

If symptoms are recorded as part of an anaphylaxis reaction as reported on the Allergic AE or in-clinic dosing form, only the single anaphylaxis reaction event will be summarized and not the individual symptoms.

All reported adverse events will be classified into SOC and preferred term using MedDRA version 19.1.

Treatment-emergent adverse events are defined as those adverse events with onset after the first dose of study product. Adverse events with onset prior to first dose of study product will be included in subject listings, but not summarized. Treatment-emergent adverse events and non-treatment-emergent adverse events will be listed separately. Treatment-emergent adverse events will be summarized for the safety population by age group (4-11 years, 12-17 years, 4-17 years), treatment group (AR101, placebo), and by study period as follows:

- Initial escalation: All events beginning after the first dose of study product on day 1 and prior to the first administration of study product at home. To avoid gaps between study periods, the first administration of study product at home is assumed to be the day after at-home study product was dispensed at Initial Escalation Day 2.
- Up-dosing: All events beginning after the first administration of study product at home during up-dosing and prior to the first dose of 300 mg at home. To avoid gaps between study periods, the first administration of 300 mg at-home dose is assumed to be the day after the clinic visit where 300 mg dose was first tolerated and at-home 300 mg study product was dispensed.
- 300 mg QD: All events beginning after the first dose of 300 mg at home and prior to exit from the study.
- Overall: Across initial escalation, up-dosing, and 300 mg QD periods (first dose to last dose).

Summaries displayed by SOC and preferred terms will be ordered by descending incidence of SOC and preferred term within each SOC. Summaries displayed by preferred term only will be ordered by descending incidence of preferred term. Summaries of the following types will be presented:

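### The SAP's 300 mg QD period has no dose-level condition, so reduced-dose and withheld time is reported as 300 mg time and the period's event rates are mixed-dose rates

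*SAP*

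**What the plan says.** SAP 7.1 has the 300 mg QD period begin with "the first dose of study product at 300 mg at home and ending with the date of the last dose of study product". It expects about 2 weeks, allows dosing to week 48 so that tolerability of 300 mg can be shown, and includes 300 mg doses taken while waiting for rollover.

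The exposure table in SAP 9.5 ends the period at "Date of last dose of study product for subjects who enter 300 mg QD study period". Duration is "calculated as the date of the last dose of study product minus the date of the first dose of study product plus 1" within the period. For adverse events, SAP 9.8.1 assigns to the period "All events beginning after the first dose of 300 mg at home and prior to exit from the study". Exposure-adjusted rates divide event counts by all subject-days in the period.

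SAP 9.5 treats one failure of 300 mg separately: "If first in-clinic 300 mg dose is not tolerated and dose is immediately reduced", the child stays in up-dosing until an in-clinic 300 mg dose is tolerated and home dosing at 300 mg follows.

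Protocol 3.3 states: "If the subject is unable to tolerate the 300 mg dose for the 2-week period, dosing may continue" up to 48 weeks after Day 1. Protocol 6.5.5.2 sends home doses that are not tolerated to the procedures of Section 6.5.5. The default action there is "Reducing dose by 1 or 2 dose levels and maintaining the reduced dose level" for at least 2 to 4 weeks. The same section provides for a two-level reduction of at least 6 weeks after two epinephrine doses for one event, and for withholding of up to 14 consecutive days.

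**The concern.** Once a child has taken one 300 mg dose at home, nothing in the SAP takes that child out of the 300 mg QD period. Weeks at 240 mg, 200 mg or less, and days with no dose, count as 300 mg QD time. Events in those weeks count as 300 mg QD events.

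The extension to week 48 exists for children who do not tolerate 300 mg, so the SAP foresees such time. SAP 9.5 is also uneven. A child whose in-clinic 300 mg dose fails goes back to up-dosing, while a child who fails at home some days later, and takes the same reduced dose, does not.

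The study is descriptive and its primary endpoint is the frequency of treatment-emergent adverse events. Exposure, rescue medication, adverse events, anaphylaxis, epinephrine use and food allergy episodes are all tabulated by this period (SAP 9.5, 9.6, 9.8.1, 9.8.3 to 9.8.5). A reader will take the label literally. Among children who would otherwise leave after 2 weeks, those who tolerate 300 mg least well stay longest and supply the mislabelled time.

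**Working it through.** The plan gives no figure for time at 300 mg, so there is none to reproduce.

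**Schedule check.** Protocol Table 2 has 11 levels of 2 weeks each. The first 300 mg dose falls at 10 × 2 = 20 weeks, and 2 weeks at 300 mg brings the total to 22. Both agree with the stated minimum durations. The room left before week 48 is 48 − 20 = 28 weeks for the fastest child and 48 − 40 = 8 weeks for the slowest.

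**One child.** I applied the SAP 9.5 duration formula to dose paths that the protocol allows. The 5 days at 300 mg before the reduction and the 14 days after it are assumptions.

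| Path between the 5 and the 14 days at 300 mg | SAP duration (days) | Days at 300 mg | Overstated by | Average mg/day |
|---|---|---|---|---|
| 240 mg for 14 days | 33 | 19 | 74% | 275 |
| 200 mg for 14 days, 240 mg for 14 | 47 | 19 | 147% | 252 |
| 200 mg for 42 days, 240 mg for 14 | 75 | 19 | 295% | 233 |
| Withheld 14 days, then 40, 80, 120, 160, 200, 240 mg for 7 days each | 75 | 19 | 295% | 154 |

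A child with 14 days at 300 mg and no reduction has 14 against 14, so nothing is overstated.

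**Whole arm.** Let f be the share of children reduced, x their weeks below 300 mg, and b the weeks at 300 mg that every child has. The share of period time not at 300 mg is f·x / (b + f·x). The values of f and x are assumptions, because the documents give neither. The value b = 2 is the planned length; b = 6 stands for rollover delay.

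| f, x | f·x | b = 2 | b = 6 |
|---|---|---|---|
| 5%, 6 weeks | 0.3 | 0.3/2.3 = 13% | 0.3/6.3 = 5% |
| 10%, 10 weeks | 1.0 | 1.0/3.0 = 33% | 1.0/7.0 = 14% |
| 15%, 16 weeks | 2.4 | 2.4/4.4 = 55% | 2.4/8.4 = 29% |

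If the reduced children have only 2 weeks at 300 mg while the others have 6, the denominator is 6(1 − f) + f(2 + x). The last column becomes 0.3/6.1 = 5%, 1.0/6.6 = 15% and 2.4/7.8 = 31%. With one default hold of 2 weeks in 5% of children, the share is 0.1/2.1 = 5% for b = 2 and 0.1/6.1 = 2% for b = 6. With f = 0 and no interruptions it is zero.

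**Rates.** Let s be the share of period days below 300 mg, and RR the event rate on those days relative to days at 300 mg. The period rate divided by the 300 mg rate is (1 − s) + s·RR.
- RR = 0.5: 0.975 at s = 0.05, 0.875 at s = 0.25.
- RR = 1: 1 throughout.
- RR = 2: 1.05 at s = 0.05, 1.25 at s = 0.25.

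The documents do not give RR. A lower dose may mean fewer reactions, but the children on it are those who had just reacted.

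**Period boundaries.** SAP 7.1 ends up-dosing at the first 300 mg dose at the site, tolerated or not. SAP 9.5 ends it at the first such dose that is tolerated and followed by home dosing, and SAP 9.8.1 agrees with 9.5. Read alone, SAP 7.1 leaves a child whose in-clinic 300 mg dose fails in neither period until home 300 mg dosing starts.

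**The case against.** The strongest defence is that a period defined by study phase is a legitimate convention in a study without hypothesis tests. It keeps poor tolerators in both arms' summaries. Up-dosing is a mixed-dose phase too. Splitting by actual dose conditions on a response to adverse events after randomisation, and the reduced-dose part may hold few placebo children. This stands, and it is why the phase-based period should remain the main summary. It does not justify a label that names one dose.

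The SAP also has partial safeguards. SAP 9.5 reports total dose, average dose per day and number of dose reductions by period, so exposure in milligrams is not overstated. These are weak detectors of time below 300 mg. In the first path above, 14 of 33 days (42%) are at 240 mg, yet the average falls only to 275 mg, and missed doses lower it as well. SAP 9.8.6 and 9.8.7 summarise dosing symptoms at each dose level. A reader might infer that this period is the only evidence on 300 mg in the study; those tables show that it is not. They give subject counts and severity, however, not rates over person-time.

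A reader might also infer that the study's count toward "at least 600 subjects treated with AR101 at 300 mg/day for 6 months" is inflated. The documents do not support that. The target relies on other studies as well, the 6-month maintenance profile is left to ARC011 with its own SAP or addendum, and no table here counts subjects toward the 600.

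Finally, the size can be pushed too high. The shares of children are assumed, 6 weeks is already longer than the default hold, and 28 weeks is only a calendar limit. Protocol 6.3.3 advises a re-escalation attempt by 4 weeks and ends dosing after three consecutive failed attempts.

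**Conclusion.** The point holds as a matter of definition. Time at reduced dose or with dosing withheld, after home dosing at 300 mg has begun, is reported as 300 mg QD. The period's duration overstates days at 300 mg for every child affected, by 74% to 295% in the paths tried. No planned summary gives days at 300 mg or event rates with matching person-time.

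For the arm as a whole the size cannot be fixed from the documents. The 13-55% and 5-29% ranges describe what the assumed shares would produce; they are not estimates of what happened, and shorter reductions give less.

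Two stronger readings are tempting. One is that the period's rates understate risk at 300 mg; the documents fix no direction. The other is that the mislabelling falls mainly on AR101. That is plausible, but the documents give no figure for it. This is a labelling and reporting defect worth correcting, not evidence that a safety signal is hidden.

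**What to change.** 1. In SAP 7.1, 9.5 and 9.8.1, keep the phase-based period as the main summary but rename it, for example *after first home 300 mg dose*.
2. In SAP 9.5, report by arm, within that period, days at 300 mg, days below 300 mg and days withheld.
3. In SAP 9.8.1, add supplementary rates of treatment-emergent adverse events by actual dose at onset, each with its own person-time. State beside them that they condition on tolerability and that the reduced-dose stratum may have few placebo subjects.
4. Reconcile SAP 7.1 with SAP 9.5 and 9.8.1 on when up-dosing ends.

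The cost is SAP wording and a little programming on dose records already used for total dose. Reported time at 300 mg becomes somewhat shorter. Treatment, visits and data collection do not change.
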